7.0 STUDY ORGANIZATION

7.1 SCHEDULE OF EVENTS

Visit ID	1	2	3	4	5	6	7	8	9
Procedure	screen/ baseline	procedure day 0	prior to discharge	7 days (± 3)	30 day FU (±10) 1mo	90 day FU (±30d) 3mo	180 day FU (±60d) 6mo	9 mo FU (±30d)	360 day FU (±60d) 12 mos.
Informed Consent (prior to study specific procedures)	X								
Eligibility Checklist (PMH, medications, verification of Inclusion and exclusion criteria)	X								
General Medical History & Cardiovascular History with CHADS2-VASC Score)	X								
LAA thrombus exclusion Transesophageal Echocardiogram (within 48 hours) or anticoagulation/LAA exclusion)	X ⁽ⁱ⁾								
Cardiac MRI or CT or Echocardiogram (showing structure & function within 1 year)	X ^(m)								
Randomization	X								
Targeted Physical Exam	X				X	X	X	X	X
12 lead EKG	X	X pre- procedure	X		X	X	X	X	X
Laboratory: CBC, Serum creatinine, and INR – (INR only if patient is taking warfarin ^(g))	X								
AF Quality of Life Questionnaire (AFEQT)	X						X	X	X
Pre-procedure 3D Mapping^(b,j)		X							
VOM Procedure w/ ETOH Injection and Post ethanol map		X ⁽ⁱ⁾							
PVAI Procedure		X							
Post Procedure 3 D Mapping		X ^(c,j)							
Follow-Up Phone Call⁽ⁱ⁾				X					
3-4 Week EKG (Event Monitor)^(d,n)							X		X
Echocardiogram , Central Reader ([name])									X ^(k)
Repeat Procedure allowed^(e)						X	X	X	
AAD Therapy	If appl.	If appl.	If appl.	If appl.	If appl.	Stop AAD ^(a)			
Anticoagulation	X	X	X	X	X	X	X	X	X
Adverse Events	X	X	X	X	X	X	X	X	X

Footnote Key

- (a) Must be in sinus rhythm prior to stopping AAD, may stop if clinically indicated
- (b) Required for both VENUS-AF and MARS-AF groups. For subjects in VENUS-AF, there should be little to no scarring for first procedure. For subjects in MARS-AF group and study patients requiring repeat procedures, maps will assess pre-existing extent of previous ablation lesions and presence or absence of PV reconnection.
- (c) To delineate extent of scar in both PVAI alone and PVAI/VOM groups.
- (d) Continuous 4 week EKG monitoring, will take place at month 6, and 12
- (e) Repeat procedures will be allowed if certain criteria met
- (f) Seven day follow-up phone call to assess post procedure symptoms.
- (g) Baseline INR must be within 24 hours prior to procedure for patients taking warfarin;
- (h) Not applicable.
- (i) For patients randomized to receive VOM ethanol infusion, and who have a vein of Marshall that can be cannulated.
- (j) For subjects who undergo repeat on-study procedures, mapping will be done a second time
- (k) Echocardiogram for LA Strain will be performed at study end at 12 months, and read centrally by core lab.
- (l) Imaging prior to enrollment is required to rule out the presence of LA appendage thrombus. Ruling out LAA thrombus can be performed by the following: TEE within 48 hours of the procedure; at least one month of oral anticoagulation prior to the procedure; or documented prior procedures of LAA occlusion or ligation.
- (m) Imaging prior to enrollment is required to rule out structural heart disease. For ruling out structural heart disease, either a cardiac MRI or CT or transthoracic echocardiogram within 1 year prior to participation in the study is sufficient.
- (n) Options for continuous EKG monitoring include: event monitoring include: external event monitor, implanted miniaturized rhythm monitor, or implanted pacemaker.

7.2 PATIENT RECRUITMENT, PROCEDURES AND FOLLOW-UP

Patients will be recruited from Cardiac Electrophysiology consultation services at all sites. Qualified, trained investigators will perform the procedures at the centers. These investigators will be unblinded. Patients will be followed up by qualified and trained at each study center.

The clinicians will follow the patients and evaluate adverse events and clinical primary endpoints.

7.3 CLINICAL RESEARCH NURSES/COORDINATORS

Each site will have designated research nurses and/or study support staff. Coordinating center may provide research nurse and/or study support staff as needed to conduct the trial efficiently. All study staff will keep in close communication with the Project Manager at the coordinating center, in order to ensure the study process runs smoothly. The coordinating center will train all study coordinators in the same manner.

7.4 DATA COORDINATING CENTER (DCC)

A DCC has been set up at the Dan L. Duncan Institute for Clinical and Translational Research at Baylor College of Medicine. Coordinators at each site will use a web-based data entry and collection system, which is capable of image collection (including maps) and FISMA-compliant. Methodist coordinating center will oversee data collection, integrity and quality. A statistician with extensive experience handling large data sets has been recruited to independently lead data analysis. He will meet periodically with DCC and lead blinded data analysis of the proposed endpoints and SAEs. Data will be reported to the DSMB with pre-specified criteria for stopping the trial if safety and futility boundaries are reached. See below in "Protection of Human Subjects".

The DCC will design, develop and maintain the secure, web-based electronic database systems for this trial. The electronic data management system (EDC) is a secure, web-based system which will require the participants to have an internet-accessible computer/tablet with an Internet browser. This electronic data management system will have logical checks and audit logs built into the system to ensure data correctness and data integrity. All automated alerts and notifications requested by the project team will be implemented in this electronic data management system. This system will also have reports and queries that are requested by the project team and the DSMB to monitor and manage the study. Also provided will be backend access to statistical software with data connectivity to facilitate data analyses. At various time points in the study, as requested by the study team, snapshots and locking of the database will occur, and clean data sets will be provided to the study team for review and data analyses.

7.5 STUDY DRUG

Investigational Product: The VOM injections will be performed using Dehydrated Alcohol Injection, USP, (multiple manufacturers). The product is commercially available and is indicated for therapeutic neurolysis in a number of medical situations, mainly for chronic pain.

Supply: The alcohol will be obtained commercially by the each site, and stored in a locked, limited access area under the appropriate temperature conditions. The number of ml used in each procedure will be documented in the surgical record by the surgeon. Site specific handling and accountability procedures, if different than above, shall be approved by the sponsor and outlined in the Clinical Trial Management Plan.

Labeling and accountability: The supply obtained for this study will be clearly marked for Investigational use per the FDA requirements, regardless of its approval status. Records will be kept of the date, patient use, and lot # of study drug used from this supply. No unused study drug will be retained. After opening, used and unused product will be destroyed on site per institutional policy. No drug supplies shall be returned to the sponsor.

Storage and Maintenance: Study drug will be stored in a cool place away from a heat source, as indicated on package insert.

Administration and Dosing: Study drug is administered intravenously. Dosing is dependent upon the surgeon achievement of sufficient neurolysis for successful ablation (up to 4 injections of 1cc ethanol).

7.6 BLINDING

Patients and personnel involved in data analysis, will be blinded to the treatment provided. Upon enrollment, the operators will be informed of the randomization outcome. After the procedure is performed, data will be collected and analyzed with treatment groups as the only identifier. The DSMB will receive the data identification for their assessment.

The primary endpoint of freedom from AF as determined by electrocardiographic monitoring by either external monitors or implanted devices will be adjudicated *in an independent and blinded manner* by the external EKG monitoring laboratory, respectively.

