5.3 INCLUSION AND EXCLUSION CRITERIA

Inclusion criteria

1. Patients between the ages of 21 and 85 years
2. Ablation History

Patients for **VENUS** must meet the following:

 - Diagnosed with symptomatic not previously ablated persistent AF,
 - AF not spontaneously converting to sinus rhythm, persisting for ≥ 7 days

Patients for **MARS** must meet the following

 - Recurrent AF or AT after a previous ablation of persistent AF at least 3 months prior to enrollment.
3. Resistant or intolerant to at least one class I, II, or III AAD
4. Patients deemed candidates for RF ablation of AF
5. Able and willing to comply with pre-, post-, and follow-up requirements.

Exclusion criteria

1. Left atrial thrombus.

LAA thrombus can be determined by pre-procedural imaging: CT, TEE or MRI. Documentation by exception (ie. no LAA thrombus on imaging reports) is permitted for determination of eligibility.
2. LA diameter greater than 65 mm on long axis parasternal view, or left atrial volume more than 200 cc.
3. Left ventricular ejection fraction < 30%.
4. Cardiac surgery within the previous 90 days.
5. Expecting cardiac transplantation or other cardiac surgery within 180 days.
6. Coronary PTCA/stenting within the previous 90 days.
7. Documented history of a thrombo-embolic event within the previous 90 days.
8. Diagnosed atrial myxoma.
9. Significant restrictive, constrictive, or chronic obstructive pulmonary disease with chronic symptoms.
10. Significant congenital anomaly or medical problem that in the opinion of the investigator would preclude enrollment
11. Women who are pregnant or who plan to become pregnant during the study.
12. Acute illness or active infection at time of index procedure documented by either pain, fever, drainage, positive culture and/or leukocytosis (WBC $> 11k/\text{mm}^3$) for which antibiotics have been or will be prescribed.
13. Creatinine $> 2.5 \text{ mg/dl}$ (or $> 221 \mu\text{mol/L}$, except for patients in dialysis).
14. Unstable angina.

15. Myocardial infarction within the previous 60 days.
16. History of blood clotting or bleeding abnormalities.
17. Contraindication to anticoagulation.
18. Life expectancy less than 1 year.
19. Uncontrolled heart failure.
20. Presence of an intramural thrombus, tumor, or other abnormality that precludes catheter introduction or positioning.
21. Presence of a condition that precludes vascular access.
22. INR greater than 3.5 within 24 hours of procedure – for patients taking warfarin.

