5.5 STUDY PROCEDURES

SCREENING/BASELINE

1. Initial assessment.

After signing informed consent, the following data will be collected; a significant medical history and recent targeted physical exam, electrocardiogram (EKG), echocardiogram within one year prior to the procedure for evaluation of cardiac structure, and function, and laboratory tests. In addition, a review of medications that patient is taking (limited to AAD and anticoagulants), and a quality of life (QOL) questionnaire especially developed for AF (AFEQT)¹¹³ will be filled out by patients.

Screening assessments performed pre-consent signature that are completed under standard of care can be included as viable source documents for patient study inclusion/exclusion and may be collected to screen potential study patients.

2. Pre-procedural imaging.

Imaging prior to enrollment is required to rule out structural heart disease and, as needed, to rule out the presence of LA appendage thrombus. *Ruling out LAA thrombus can be performed by the following: TEE, CT or MRI within 48 hours of the*

procedure; at least one month of oral anticoagulation prior to the procedure; or documented prior procedures of LAA occlusion or ligation. For ruling out structural heart disease, either a cardiac MRI, CT or transthoracic echocardiogram within 1 year prior to participation in the study is sufficient. Documentation by exception (ie. no LAA thrombus documented on imaging report) is permitted for determination of eligibility. Left atrial diameter and estimated left atrial volume will be obtained from any of these diagnostic modalities. There is no specific requirement for a pre-ablation CT or MR, since anatomical details of the LA can be obtained intra-procedurally with current mapping systems.

3 Randomization.

Randomization should take place after confirmation that all inclusion/exclusion criteria are met and measurements of LA volume are obtained. Patients will be randomized in a 1.15:1 fashion (to account for an 85% technical feasibility of the VOM procedure) to receive either VOM-PV or the conventional PVAI. Patients will be blinded to the randomization outcome.

PROCEDURE/DAY 0:

1 PVAI procedure

As part of a conventional catheter ablation of AF the following will be performed, all considered standard of care:

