6.0 STATISTICAL CONSIDERATIONS

A) Assumptions.

Single-procedure versus multiple-procedure success. Our initial preliminary data suggested an overall procedure success of 45% in patients undergoing PVAI and 61% for those undergoing VOM-PV (difference of 16%). This included patients with repeat procedures performed in some, but not all of the failed procedures (45% all patients in the PVAI group and 30% in the VOM-PV group). **The single-procedure success was 38% in patients undergoing PVAI and 56% in patients undergoing VOM-PV** (difference of 18%). Thus, the endpoint of single-procedure success is likely to show greater differences amongst groups.

Mortality. The expected mortality is low in this study as it has been in AF ablation trials.

Mortality will be recorded as a safety endpoint.

One-year follow-up time. In previous versions of the protocol, additional follow-up time (up to 15 months) was included in the VENUS trial, in order to accommodate for appropriate follow-up of patients undergoing repeat procedures. Therefore, a trial duration of 12 months is sufficient if just single-procedure success is the primary efficacy endpoint. Procedural failures (events counted as the primary efficacy endpoint) occur mostly during the first year. Additionally, 12-month follow-up is consistent with the recommendations for clinical trials in AF by the HRS/EHRA/ECAS Catheter and Surgical Ablation consensus document.²

Unknown classification as success or failure. Patients who cannot be classified as successes or failures on the primary efficacy endpoint will be excluded from the primary analysis.

B) VENUS Group Sequential Clinical Trial Design

Power and sample size determination. Group sequential two proportions power analysis using simulation was performed using PASS V12 (Kaysville, UT). The following assumptions were made:

- Response rate in PV-VOM: $p_1=0.56$
- Response rate in PVAI: $p_2= 0.38$
- Hypotheses: $H_0: p_1= p_2$; $H_1: p_1 \neq p_2$
- Test Statistic: Z-Test (Unpooled)
- Zero Adjustment Method: None
- Alpha-Spending Function: O'Brien-Fleming Analog
- Beta-Spending Function: None
- Futility Boundary Type: None
- Number of Looks: 3
- Simulations: 100000

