7.8.2 Serious Adverse Events (SAE) Reporting

An adverse event that meets one or more of the following criteria/outcomes will be classified as serious: These events will be treated accordingly and reported per local & federal regulations and institutional policies & requirements.

- Results in a life-threatening illness or injury.
- Results in permanent impairment of a body structure or a body function.
- Requires inpatient hospitalization ≥ 24 hours (other than the ablation procedure) or prolongation of existing hospitalization.
- Requires a medical or surgical intervention to prevent permanent impairment to body structure.
- Death

SAE's will be reported in accordance with current institutional policies.

NOTE: Unexpected serious adverse events deemed related, probably or possibly related to the VOM study procedure will warrant a hold on the study until further review and approval by the IRB and DSMB.

Screen Failure AEs will be documented as follows: Adverse events that occur for subjects prior to the intervention, will be documented in the study record and will not be reported to the IRB or sponsor (HMRI) unless unexpected or the PI determines the event should be reported to the IRB as non-study intervention related event. Subjects who are deemed screen failures and experience an event that meets the general SAE criteria will be followed until resolution of the event and those events will be reported to HMRI as the sponsor of the IND, and to the IRB per institutional policies for reporting SAE's.

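### Operators may know the arm before procedure-timed exclusions are settled, and no rule keeps randomised but untreated patients in the primary analysis

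*Combined protocol and SAP*

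**What the plan says.** **Timing of randomisation.** In the Schedule of Events (section 7.1) the row "Randomization" is marked only under Visit 1 (screen/baseline), not under Visit 2 (procedure day 0). Section 5.5 also lists it under Screening/Baseline and sets the order: "Randomization should take place after confirmation that all inclusion/exclusion criteria are met and measurements of LA volume are obtained". No maximum interval from randomisation to procedure is stated.

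**Who knows the arm, and when.** Section 7.6: "Upon enrollment, the operators will be informed of the randomization outcome". Patients and data analysts are to be blinded, and the synopsis also blinds the co-investigator who follows the electrocardiographic data. The operator is not blinded.

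**Exclusions tied to the procedure (section 5.3).** Item 12: "Acute illness or active infection at time of index procedure". Item 22, for patients on warfarin: "INR greater than 3.5 within 24 hours of procedure". Footnote (g) of section 7.1 repeats the INR timing: "Baseline INR must be within 24 hours prior to procedure for patients taking warfarin".

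**Who is analysed.** Section 6.0 A: "Patients who cannot be classified as successes or failures on the primary efficacy endpoint will be excluded from the primary analysis". Analysis by original randomisation group is stated only in the cross-over paragraphs of sections 5.7 and 5.8. Multiple imputation is a secondary analysis (section 6.0, Missing data). No analysis population is defined, and no rule covers a patient who is randomised but never has the procedure.

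**The concern.** Randomisation protects the comparison only if nobody who knows the arm can decide whether a patient counts. Here the operator may know the arm while item 12 is still open, and part of that item (pain, fever) calls for judgement. The VOM arm adds instrumentation of the coronary sinus and VOM and, in the pilot experience of section 7.8, about 45 minutes. The threshold for cancelling could therefore differ between arms.

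If cancelled patients are not followed, they have no classifiable outcome and drop out of the primary comparison. If those lost from one arm have a worse prognosis than those who stay, the difference in success rates is biased. The unadjusted Z-test can neither detect nor correct this.

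**Working it through.** **1. The plan's own figure.** Inputs from section 6.0 B: 180 VOM-PV and 156 PVAI patients, success 0.56 and 0.38, unpooled Z-test, boundaries 3.953, 2.543 and 2.011.

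- SE = √(0.56×0.44/180 + 0.38×0.62/156) = 0.0537
- 0.18/0.0537 = 3.35; 3.35 − 2.011 = 1.34; Φ(1.34) = 0.910
- Simulation of the three-look design (200,000 runs): power 0.9095, against 0.909 stated. With both arms at 0.38, the two-sided error is 0.0496 and the chance of a false finding for VOM is 0.025.

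The stated design is reproduced.

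**2. The passages side by side.**

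| Step | Source | Timing |
|---|---|---|
| All criteria confirmed, then randomise | 5.5 | Before the procedure, interval open |
| Randomisation marked | 7.1 | Visit 1 only |
| Operator told the arm | 7.6 | On enrolment |
| INR (warfarin patients) | 5.3 item 22; 7.1 footnote (g) | Within 24 hours before the procedure |
| Acute illness or infection | 5.3 item 12 | At the procedure |

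The INR check can precede randomisation if Visit 1 runs into the last 24 hours. Item 12 can be confirmed beforehand only if randomisation takes place at the procedure, which the schedule does not show.

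**3. Illustration of selective loss.** The documents give no loss rate, so the loss fraction f and the success rate q among those lost are assumptions. With 0.38 in both arms and loss from the VOM arm only:

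observed VOM rate = (0.38 − f×q)/(1 − f); shift = observed rate − 0.38.

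| f (of 180) | q | Observed VOM rate | Shift (points) |
|---|---|---|---|
| 2% (3.6 patients) | 0.20 | 0.376/0.98 = 0.3837 | +0.4 |
| 2% | 0.10 | 0.378/0.98 = 0.3857 | +0.6 |
| 5% (9 patients) | 0.20 | 0.370/0.95 = 0.3895 | +0.9 |
| 5% | 0.10 | 0.375/0.95 = 0.3947 | +1.5 |
| 5% | 0.30 | 0.365/0.95 = 0.3842 | +0.4 |
| any | 0.38 | 0.3800 | 0 |

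The same loss in the PVAI arm gives the same shift with the opposite sign.

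For scale, the null standard error at the final look is √(0.38×0.62×(1/180 + 1/156)) = 0.053. A shift of 0.4 to 1.5 points is therefore about 0.07 to 0.28 standard errors, against a design difference of 18 points.

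**4. Effect of keeping untreated patients and counting them as failures** (simulated, true rates 0.56 and 0.38):

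| Untreated | Both arms equally | VOM arm only |
|---|---|---|
| 2% | power 90.0% | 87.1% |
| 5% | 88.2% | 79.5% |

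If randomisation follows the last check and nobody is lost, power stays at 91%.

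**The case against.** The strongest reply is that section 5.5 already sets the order: no randomisation until every criterion is met. Visit 1 has no day number, and its column also holds the INR check with its 24-hour limit. Visit 1 could therefore run to the day before the procedure, with randomisation last. This stands for the INR, which also concerns only patients on warfarin. It does not fully stand for item 12, and it says nothing about a procedure cancelled after randomisation for any other reason.

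Cancellation also need not mean exclusion. A postponed patient can still be treated. A cancelled patient who is followed can be classified, and persistent AF after month 3 would probably count as a failure, against the patient's own arm. That is correct, but the plan does not say that such patients are followed.

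The planning simulations in section 6.0 cover 0-20% missing outcomes, drawing missing results from the opposing arm's success rate. They apply the same missing fraction to both arms and do not change the primary analysis rule. Eligibility monitoring (section 9.3) and audit logs (section 7.4) help, but they do not define an analysis set.

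A reader might infer more than the documents support:

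- **Left atrial appendage thrombus as a late check.** Footnote (l) of section 7.1 places this imaging before enrolment, and sections 5.5 and 7.1 allow routes without imaging.
- **Exclusions 20 and 21 as findings made only in the laboratory.** No passage says so.
- **Failed VOM cannulation as a way out of the trial.** It is not an exclusion; the 1.15:1 allocation allows for it.
- **Screen failure continuing after randomisation.** Section 7.8.2 says "Adverse events that occur for subjects prior to the intervention, will be documented in the study record", but this is a reporting rule. Adverse event collection starts at consent (section 7.8.1), so the sentence can refer to the time before randomisation.

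**Conclusion.** The point holds as a gap in conduct and analysis. Sections 5.5, 7.1 and 7.6 do not settle whether the arm is disclosed before or after the last procedure-timed check, and nothing in section 6.0 keeps a randomised but untreated patient in the primary comparison. An unblinded operator could therefore influence who is analysed.

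Removal of such patients is an inference from the rule on unclassifiable outcomes and the absence of a defined population. No passage says that patients found ineligible late are removed.

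The size is unknown. The +0.4 to +1.5 points rest on three assumptions: loss in the VOM arm only, 2-5% of that arm lost, and success of 10-20% among those lost. Nothing in the documents links a raised INR or an acute infection to ablation success. It would go too far to read the illustration as an estimate of bias, or as evidence that the type I error is inflated in favour of VOM.

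**What to change.** 1. Reconcile sections 5.5 (item 3), 7.1 and 7.6. Move the randomisation mark to Visit 2 and state that randomisation and disclosure to the operator take place on the procedure day, after the last procedure-timed eligibility checks (acute illness, and INR where applicable) have been entered in the web-based system.
2. In section 6.0 A, define the primary population as all randomised patients in their assigned arm, including those whose procedure is cancelled. Follow these patients for outcome and state in advance how they are classified. Amend the rule on unclassifiable patients to match.
3. Report the number of randomised but untreated patients, with reasons, by arm.

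**Cost.** The change needs protocol wording and a change of visit in the existing system. VOM supplies and laboratory time must be available for every case until the arm is shown. If untreated patients count as failures, power falls slightly when the loss is small and balanced (90.0% at 2%, 88.2% at 5%) and more if it falls only on the VOM arm (87.1% and 79.5%). Randomising late should keep such losses few.
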